11.2 Secondary Technical Efficacy Endpoint(s) Analysis

- % detection of false positives (FP), comparison of NB-IS TCD with TTE
- % detection of true negatives (TN) (specificity), comparison of NB-IS TCD with TTE
- % detection of false negatives (FN), comparison of NB-IS TCD with TTE
- Positive Predictive Value (PPV), comparison of NB-IS TCD with TTE
- Negative Predictive Value (NPV), comparison of NB-IS TCD with TTE
- Demonstration of NB-IS TCD diagnostic performance to SOC TCD for diagnostic accuracy parameters (sensitivity, specificity, PPV, NPV).
 - o If bilateral signals are found, the microbubble count will be sum across both vessels.
 - o If only a unilateral signal is found, the microbubble count will be doubled for the total count.
 - Spencer Logarithmic Scale (SLS) and International Consensus Criteria (ICC) gradings from the Imaging Core Lab for NB-IS TCD and SOC TCD will be compared for analysis.
- Demonstration of NB-IS TCD diagnostic performance targeting to transesophageal echocardiography (TEE) for diagnostic accuracy parameters (sensitivity, specificity, PPV, NPV).
- % detection of intervenable shunts, comparison of NB-IS TCD with TTE
 - For NB-IS TCD, Grade 3 and above (>30 microbubbles) on the Spencer Logarithmic Scale (SLS) and International Consensus Criteria (ICC) considered intervenable shunt¹⁰.
 - o For TTE, >20 microbubbles per 2016 American Society of Echocardiography Guidelines and Standards²³ considered intervenable shunt.
- NB-IS TCD No Window rate performance to SOC TCD parameters (including both unilateral and bilateral absent acoustic windows).
- % success rate of NB-IS TCD
 - o Incidence of failed registrations (device unable to register)
 - Incidence of bilateral signals not found (no evaluable signals found both sides)
 - Incidence of unilateral signals not found (evaluable signal found on one side)
 - An adequate, evaluable, and complete study is defined for the purposes of this protocol as successful acquisition of a unilateral signal at 40-65mm depth range recorded for the duration of the bubble study in the Resting position and with Valsalva Maneuver.
- Incidence of device malfunctions

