2.3 Limitations

Although TTE is the most frequently used non-invasive technique for the assessment of RLS, it is limited by its dependence on the expertise of the technician performing the exam. Furthermore, its moderate sensitivity (45.1%) but high specificity (99.6%) in RLS indication should not be relied upon in the determination of treatment for ESUS patients⁶.

While TEE is considered the gold standard for visualization of the PFO after its presence has been indicated, its invasive nature can make it difficult for the patient to comply with the necessary steps for the VM. Although TEE is contraindicated in patients with dysphagia or esophageal issues, its sensitivity and specificity are 95% and 95% for indication of RLS⁷.

Like TTE, the diagnostic value of TCD is limited by the expertise of the technician performing the exam and the presence of optimal acoustic windows. Signal acquisition is a well-documented obstacle in TCD evaluation regardless of pathology and is no different in the case of RLS

DWF-C0001-001 CONFIDENTIAL Page 14 of 44

assessment⁸. However, unlike TTE, TCD has shown excellent sensitivity and specificity in RLS detection (96.1% and 92.4%, respectively) against the gold standard of TEE⁶.

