4.1 Primary Efficacy Endpoint

 % detection of RLS/PFO with NB-IS TCD compared against standard of care Transthoracic Echocardiography (TTE)

4.2 Secondary Technical Efficacy Endpoints:

- % agreement for detection of RLS/PFO with NB-IS TCD vs SOC TCD
- % agreement for detection of RLS/PFO with NB-IS TCD vs Transesophageal Echocardiography (TEE)
- % agreement for detection of clinically significant shunts with NB-IS TCD vs TTE
- No window rate (including both unilateral and bilateral absent acoustic windows)
- Success rate of the NB-IS TCD
- Incidence of NB-IS device malfunctions

4.3 Exploratory Endpoints:

 Development of an automated algorithm for Spencer Logarithmic Scale¹⁰ and International Consensus Criteria grading of RLS¹¹

4.4 Primary Safety Endpoint:

Incidence of device-related serious adverse events.

4.5 Secondary Safety Endpoints:

Incidence of procedure-related adverse events related to agitated saline injection before and after VM (headache, allergic reactions, new onset neurological deficit, ischemic stroke, TIA or

DWF-C0001-001 CONFIDENTIAL Page 18 of 44

pulmonary embolism complicating agitated saline contrast injection, etc) will be closely monitored and prospectively collected¹².

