11.5 RLS/PFO Validation and Analysis

Evaluation of correlation between diagnostic imaging standard of care (SOC TCD/TTE/TEE) and NB-IS TCD diagnostic performance by an independent core laboratory. Success criteria will include clinical validation of NB-IS TCD for RLS/PFO detection targeting (i) 40% increase in NB-IS TCD sensitivity compared to TTE sensitivity and (ii) NB-IS TCD sensitivity ≥ 90% compared to SOC TCD sensitivity.

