11.6 Sample Size Calculation

The present study was powered based on the results of a recent meta-analysis reporting a pooled TCD sensitivity of 96.1% for RLS detection, while the pooled TTE sensitivity was estimated at 45.1% (absolute difference of 51%)⁶. For power calculations, we used a more moderate effect size of 40% increase in the sensitivity of NB-IS TCD compared to TTE.

A sample size of 100 subjects achieves 90% power to detect a difference of 40% between two diagnostic tests whose sensitivities are 90% (TCD) and 50% (TTE). This procedure uses a two-sided McNemar test with a significance level of 0.05. The mean prevalence of PFO in the population of patients with cryptogenic stroke is at least 30%². The proportion of discordant pairs has been set at 0.500.

[figure not shown]
		Sensitivity	ity Sensitivity Proportion					
		of Test 1	of Test 2		Discordant	Prevalence		
Power	N	Se1	Se2	Se1-Se2	D	Р	Alpha	Beta
0.00000	10	0.900	0.500	0.400	0.500	0.300	0.05000	
	1.00000							
0.00830	20	0.900	0.500	0.400	0.500	0.300	0.05000	
	0.99170							
0.12990	30	0.900	0.500	0.400	0.500	0.300	0.05000	
	0.87010							
0.32013	40	0.900	0.500	0.400	0.500	0.300	0.05000	
	0.67987							
0.49003	50	0.900	0.500	0.400	0.500	0.300	0.05000	
	0.50997							
0.62345	60	0.900	0.500	0.400	0.500	0.300	0.05000	
	0.37655							
0.72404	70	0.900	0.500	0.400	0.500	0.300	0.05000	
	0.27596							
0.79937	80	0.900	0.500	0.400	0.500	0.300	0.05000	
	0.20063							
0.85654	90	0.900	0.500	0.400	0.500	0.300	0.05000	
	0.14346							
0.89995	100	0.900	0.500	0.400	0.500	0.300	0.05000	
	0.10005							
0.93182	110	0.900	0.500	0.400	0.500	0.300	0.05000	

DWF-C0001-001 CONFIDENTIAL Page 37 of 44

Protocol ID: NA-07BBL-01 Version Date: August 2, 2021

	0.06818						
0.95405	120	0.900	0.500	0.400	0.500	0.300	0.05000
	0.04595						
0.96898	130	0.900	0.500	0.400	0.500	0.300	0.05000
	0.03102						
0.97890	140	0.900	0.500	0.400	0.500	0.300	0.05000
	0.02110						
0.98561	150	0.900	0.500	0.400	0.500	0.300	0.05000
	0.01439						

 $\label{eq:vsN} vs~N$ Se1=0.900 Se2=0.500 D=0.500 α =0.050 P=0.300 2-Sided McNemars Test

Given previous reports indicating a prevalence of suboptimal transtemporal windows in 5% of Hispanic²⁰, 5% of Caucasian²¹, 9% in African American¹⁹ and 14% of Asian²² individuals aged <60 years, we increased our projected sample size by 20% (n=120). In addition, the final sample size

DWF-C0001-001 CONFIDENTIAL Page 38 of 44

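### Section 11.2 names no reference standard for its NB-IS versus TTE accuracy measures; if TTE serves as the reference, specificity and PPV are materially understated and NPV is overstated.

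*Combined protocol and SAP*

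**What the plan says.** Section 11.2 opens its secondary analyses with five lines on NB-IS and TTE: false positives, specificity, false negatives, PPV and NPV. Two of them read "detection of true negatives (TN) (specificity), comparison of NB-IS TCD with TTE" and "Positive Predictive Value (PPV), comparison of NB-IS TCD with TTE". None states what determines true shunt status. Later lines of the same section plan sensitivity, specificity, PPV and NPV in relation to SOC TCD and, separately, to TEE.

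On TTE itself, section 2.3 says "its moderate sensitivity (45.1%) but high specificity (99.6%) in RLS indication should not be relied upon" when treatment is decided. The same section reports TCD accuracy for shunt "detection (96.1% and 92.4%, respectively) against the gold standard of TEE". Section 11.5 sets as a success criterion a "40% increase in NB-IS TCD sensitivity compared to TTE sensitivity", and section 11.6 plans on 90% for TCD and 50% for TTE.

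Section 4.2 does not list specificity or predictive values. Its endpoints against SOC TCD and TEE are percent agreement. Its only endpoint against TTE is "agreement for detection of clinically significant shunts with NB-IS TCD vs TTE". Overall shunt detection relative to TTE is the primary endpoint in section 4.1.

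**The concern.** TTE has two incompatible roles. In sections 11.5 and 11.6 it is a competitor with a sensitivity of its own, which a reference standard cannot have: scored against itself, its sensitivity would be 100%. In the five lines of section 11.2 it is the only modality named, so an analyst filling in a 2x2 table would most readily put it in the reference column.

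In that case a subject with a real shunt, positive on NB-IS and negative on TTE, supports the primary hypothesis and also counts as a device error in the secondary analysis. The more shunts NB-IS finds beyond TTE, the worse its specificity and PPV look. The report of a pivotal study would then carry a low specificity and PPV that mostly reflect TTE misses.

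**Working it through.** **1. The plan's own power figure.** Inputs from section 11.6: sensitivities 0.90 and 0.50, discordant proportion 0.500, prevalence 0.30, two-sided McNemar test at 0.05, N = 100. Subjects with a shunt: 0.30 × 100 = 30. Discordant pairs follow Binomial(30, 0.50). The NB-IS-only and TTE-only shares sum to 0.50 and differ by 0.40, so they are 0.45 and 0.05, and NB-IS takes 0.45/0.50 = 0.90 of the discordant pairs. Rejecting when the exact two-sided binomial p is at most 0.05 gives power 0.89995, as tabulated. Eight other rows of the table (N = 10, 20, 30, 40, 50, 80, 120, 150) also match. The inputs are therefore read as the plan intends.

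**2. The same inputs with TTE as reference.** Assume neither test gives false positives. Among subjects with a shunt, both tests are positive in 0.90 − 0.45 = 0.45 and both negative in 0.05. Proportions of all subjects:

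| | TTE+ | TTE− |
|---|---|---|
| NB-IS+ | 0.30 × 0.45 = 0.135 | 0.30 × 0.45 = 0.135 |
| NB-IS− | 0.30 × 0.05 = 0.015 | 0.30 × 0.05 + 0.70 = 0.715 |

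- Specificity: 0.715/(0.135 + 0.715) = 84.1% (true 100%).
- PPV: 0.135/(0.135 + 0.135) = 50.0% (true 100%).
- NPV: 0.715/(0.015 + 0.715) = 97.9% (true 0.70/0.73 = 95.9%).
- False-negative rate: 0.015/(0.135 + 0.015) = 10% (true 10%).

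True shunts labelled false positive are 13.5 per 100 subjects, or about 20 of 150.

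**3. With imperfect specificity.** NB-IS: sensitivity 90% (section 11.6) and specificity 92.4% (the TCD value in section 2.3). TTE: 45.1% and 99.6% (section 2.3). Prevalence 30% and errors independent given true status; both are assumptions.

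- NB-IS+/TTE+: 0.30 × 0.90 × 0.451 + 0.70 × 0.076 × 0.004 = 0.1220
- NB-IS+/TTE−: 0.30 × 0.90 × 0.549 + 0.70 × 0.076 × 0.996 = 0.2012
- NB-IS−/TTE+: 0.30 × 0.10 × 0.451 + 0.70 × 0.924 × 0.004 = 0.0161
- NB-IS−/TTE−: 0.30 × 0.10 × 0.549 + 0.70 × 0.924 × 0.996 = 0.6607

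| Measure | Against TTE | True |
|---|---|---|
| Specificity | 0.6607/0.8619 = 76.7% | 92.4% |
| PPV | 0.1220/0.3232 = 37.7% | 0.27/0.3232 = 83.5% |
| NPV | 0.6607/0.6768 = 97.6% | 0.6468/0.6768 = 95.6% |
| False-negative rate | 0.0161/0.1381 = 11.7% | 10% |

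Of the labelled false positives, 0.1482/0.2012 = 74% are real shunts.

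**4. Sensitivity to the assumptions.** Take NB-IS at 96.1%/92.4% and TTE at 45.1%/99.6%, both from section 2.3. At 30% prevalence, apparent specificity and PPV are 75.5% and 38.1% with independent errors, and 76.4% and 40.4% with maximal overlap of errors. Over an assumed prevalence of 25% to 50% with independent errors, apparent specificity runs from 78.7% down to 61.0% and PPV from 36.5% to 41.8%. The direction does not change.

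**The case against.** The strongest reply is that section 11.2 never calls TTE the reference. The wording of the five lines also allows a side-by-side comparison of two tests, each scored against a third standard. Sections 11.5 and 11.6 point that way, and so does the intervenable-shunt line of section 11.2, which gives NB-IS and TTE separate bubble thresholds. On that reading the bias does not arise. This stands as far as it goes: a reader might infer that the plan makes TTE the reference, and the text does not say so.

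The reply does not settle the matter, because no third standard is available for all subjects. The notes to the schedule of assessments collect TEE in the main study only if performed, and later subjects may have TTE instead. Section 11.4 has the core laboratory read every modality but does not ask it to determine true shunt status. An analyst must either use TTE or devise a reference.

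Three further inferences go too far.

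- All five measures might be thought to penalise the device. Neither NPV nor the false-negative rate uses the NB-IS+/TTE− cell. NPV in fact flatters the device, because shunts missed by both tests count as true negatives.
- The false-positive rate might be thought not to be estimated anywhere. Section 11.2 already plans specificity and PPV against TEE.
- Section 4.2 might be read as making percent agreement the general endpoint against TTE. It does so only for clinically significant shunts.

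It is also fair to say that these are secondary measures without a test or threshold, and that both success criteria in section 11.5 concern sensitivity.

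**Conclusion.** The point holds in a conditional form. No reference standard is named for the five NB-IS and TTE lines of section 11.2, and TTE's role there does not fit its role in sections 11.5 and 11.6. If TTE is used as the reference, specificity and PPV are understated by an amount that would change how a reader judges the device. On the plan's own inputs the shortfall is about 16 and 50 percentage points (100 − 84.1 and 100 − 50.0), assuming perfect specificity for both tests. In the imperfect-specificity case it is about 16 and 46 points (92.4 − 76.7 and 83.5 − 37.7), assuming 30% prevalence and independent errors. NPV is overstated by about 2 points in both cases. The study's success criteria are untouched; what is at risk is the interpretation of the secondary accuracy results. The change should be made, but it does not call the design into question.

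**What to change.** In section 11.2:

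- Replace the five TTE lines with the full NB-IS by TTE 2x2 table, reported as positive and negative percent agreement with 95% CIs. State that no conclusion on false positives, specificity or predictive values is drawn from it.
- Report specificity, PPV and NPV against TEE, as the section already plans.
- Keep the SOC TCD comparison, labelled as agreement in line with section 4.2.
- For NB-IS-positive, TTE-negative subjects who had TEE, report the number and proportion confirmed by TEE.
- Add the overall agreement with TTE to section 4.2, which now lists it only for clinically significant shunts.

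The cost is a change of wording; no new data are needed. The drawback is that the TEE-based figures rest on a smaller subset, referred under each institution's usual practice (section 6.12.6). Their intervals will be wider and they are open to verification bias. The report should say so and give the number of subjects with TEE in each cell of the NB-IS by TTE table.

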1 PROTOCOL SYNOPSIS

Protocol Synopsis:				
NovaSignal Corp. [name]	Protocol No.: NA-07BBL-01			
	Regulatory Class: II			
	Study Device(s): NeuralBot Investigational System (NB-IS)			
	Development Phase: Pivotal			

Study Title:

Robotic TCD Ultrasound Bubble Study Compared to Transthoracic Echocardiography for Detection of Right to Left Shunt

Overall Study Design:

This study is a multi-center, prospective, single-arm, non-significant risk (NSR) device study in which up to 150 evaluable subjects with embolic stroke of undetermined source (ESUS) according to standardized criteria¹³ will be evaluated with NB-IS TCD and standard of care TTE to screen for right to left shunt (RLS) or patent foramen ovale (PFO). Additionally, up to 150 evaluable subjects will be evaluated with NB-IS TCD and standard of care TTE or TEE.

Objective:

To evaluate the shunt detection rate of the NeuralBot Investigational System (NB-IS) TCD relative to standard of care diagnostic techniques (transthoracic echocardiography (TTE), transesophageal echocardiography (TEE), and standard transcranial Doppler ultrasound (TCD) and to assess the safety, accuracy and usability of the NB-IS device.

Number of Subjects:

TTE Main Study: Up to 150 subjects with suspected RLS/PFO receiving TTE TEE Sub-Study: Up to 150 subjects with suspected RLS/PFO receiving TTE or TEE

Number of Sites:

Up to 7 centers total (US)

Duration of Study Participation:

- Enrollment: approximately 9-15 months
- Participant duration: 1-3 days (screening, NB-IS TCD, TCD, TTE, TEE); 1-60 days (follow-up)

Primary Efficacy Endpoint:

 % detection of RLS/PFO with NB-IS TCD compared against standard of care Transthoracic Echocardiography (TTE)

Secondary Technical Efficacy Endpoint:

- % agreement for detection of RLS/PFO with NB-IS TCD vs SOC TCD
- % agreement for detection of RLS/PFO with NB-IS TCD vs Transesophageal Echocardiography (TEE)
- % agreement for detection of intervenable shunts with NB-IS TCD vs TTE
- No window rate (including both unilateral and bilateral absent acoustic windows)
- Success rate of the NB-IS TCD

Protocol Synopsis:				
Study Sponsor: NovaSignal Corp. [name]	Protocol No.: NA-07BBL-01			
	Regulatory Class: II			
	Study Device(s): NeuralBot Investigational System (NB-IS)			
	Development Phase: Pivotal			

Incidence of device malfunctions

Exploratory Endpoints:

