5.1 Study Population Size

To ensure the study is adequately powered, up to 150 subjects will be enrolled at up to 7 centers in the US. The estimation of this sample size has taken into account the prevalence of suboptimal transtemporal windows and potential dropouts.

Once the 150 TTE subjects are enrolled, the study will continue to enroll up to another 150 subjects that received a TTE or TEE until enough TTE subjects have been enrolled in the different grades of the International Consensus Criteria (0,1,2,3) across the TTE Main Study and TTE/TEE Sub Study combined.

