13.2 International Consensus Criteria (ICC)¹¹

ICC GRADE	ICC Microembolic Signal (MES) Count
Grade 0	No MES
Grade 1	1 – 20 MES
Grade 2	> 20 MES or "shower" appearance
Grade 3	"curtain" appearance of MES

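### The NB-IS TCD cut for an intervenable shunt (Section 11.2) matches the Spencer scale but contradicts the ICC table, and no section says which scale governs

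*Combined protocol and SAP*

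**What the plan says.** Section 11.2 defines the classification for the investigational device: "For NB-IS TCD, Grade 3 and above (>30 microbubbles) on the Spencer Logarithmic Scale (SLS) and International Consensus Criteria (ICC) considered intervenable" (shunt), citing reference 10, which is the source of the SLS. For TTE the same section uses a single count, more than 20 microbubbles.

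The two scales are tabulated in the appendix. In 13.1 (SLS), Grade 2 ends at 30 signals, Grade 3 covers 31 to 100, Grade 4 covers 101 to 300, and Grade 5 is above 300. In 13.2 (ICC), Grade 1 ends at 20 signals and Grade 2 is "> 20 MES or 'shower' appearance" with no upper count. ICC Grade 3 is a curtain appearance with no count attached, and it is the top grade. Section 5.1 likewise lists ICC grades 0 to 3 only.

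The endpoint listings give neither a cut nor a scale, and they use different labels. The synopsis has "agreement for detection of intervenable shunts with NB-IS TCD vs TTE" and Section 4.2 has "agreement for detection of clinically significant shunts with NB-IS TCD vs TTE". On grading, Section 11.2 says that SLS and ICC "gradings from the Imaging Core Lab for NB-IS TCD and SOC TCD will be compared for analysis". Section 11.4 lets core-lab readings override local ones.

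**The concern.** The sentence in 11.2 treats Grade 3 and above, more than 30 microbubbles, SLS and ICC as one rule. By the protocol's own tables they are not one rule. The sentence can be read as the count or SLS rule, as the ICC Grade 3 rule, as both required, or as either sufficient. These readings disagree on recordings with many signals but no curtain.

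If the choice is left open, whoever runs the analysis picks the definition of a named secondary endpoint with both grades already in hand. The TTE side has one clear cut, so the freedom lies only on the side of the device under evaluation.

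**Working it through.** **Step 1: is a count above 30 the same as Grade 3 or above?** For the SLS, yes: Grade 2 stops at 30 and Grade 3 starts at 31, and this held at every count checked from 0 to 1000. For the ICC, no: without a curtain, every count from 31 up to the 1000 tested is Grade 2.

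**Step 2: apply each reading of the 11.2 sentence to the appendix tables.**

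| Recording | SLS grade | ICC grade | Count >30, or SLS ≥3 | ICC 3 | Both required | Either sufficient |
|---|---|---|---|---|---|---|
| 30 or fewer, no curtain | 0–2 | 0–2 | no | no | no | no |
| 31–100, no curtain | 3 | 2 | **yes** | **no** | **no** | **yes** |
| 101–300, no curtain | 4 | 2 | **yes** | **no** | **no** | **yes** |
| Above 300, no curtain | 5 | 2 | **yes** | **no** | **no** | **yes** |
| Above 30, curtain | 3–5 | 3 | yes | yes | yes | yes |
| 30 or fewer, curtain | 1–2 | 3 | no | yes | no | yes |

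Example: 50 signals without a curtain is SLS Grade 3 and ICC Grade 2. It is intervenable by count and by SLS, and not intervenable by ICC Grade 3 or if both are required. The count/SLS reading departs from both the ICC-only and the both-required readings on the no-curtain rows above 30. The last row is a further disagreement that the text does not exclude, because ICC Grade 3 has no minimum count; it may be rare.

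**Step 3: the unilateral rule.** Section 11.2 says: "If only a unilateral signal is found, the microbubble count will be doubled for the total count". This line stands under the comparison with SOC TCD, so its use for the present endpoint is an assumption. If it applies, 16 signals on one side become 2 × 16 = 32, which is SLS Grade 3 and ICC Grade 2. Fifteen become 30, which is Grade 2 on both.

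**Step 4: effect per affected subject on the NB-IS intervenable rate.** The rate moves by 1/N, where N is the number analysed, or by 1/(0.30 × N) if the denominator is shunt-positive subjects at the 30% prevalence in Section 11.6.

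| N | Source | 1/N | 0.30 × N | 1/(0.30 × N) |
|---|---|---|---|---|
| 100 | Section 11.6, before inflation | 1.0 point | 30 | 3.3 points |
| 150 | Section 5, main study | 0.67 point | 45 | 2.2 points |
| 300 | 150 + 150, if every added subject had TTE | 0.33 point | 90 | 1.1 points |

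As an illustration only: if 5 to 15 of the 45 shunt-positive subjects had more than 30 signals and no curtain, the rate would differ between readings by 5/45 = 11 points to 15/45 = 33 points. The 5 and 15 are assumed; nothing in the documents supplies them.

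**Step 5: effect on agreement with TTE.** Let k subjects have more than 30 signals and no curtain, and let a of them be intervenable on TTE. Moving from the count/SLS reading to ICC Grade 3 gains k − a agreements and loses a, a net change of (k − 2a)/N for these recordings. This lies between −k/N and +k/N and is zero when a = k/2. The direction therefore cannot be stated in advance.

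**The case against.** The strongest reply is that the sentence resolves itself. Its only number, more than 30, is the SLS Grade 3 boundary; its citation is the SLS source; and the parallel TTE rule is also a plain count. An analyst using the one number given would call 50 signals intervenable, and the ICC is probably a stray scale name. This makes the SLS the likeliest intention. But the sentence names the ICC, and the ICC is not incidental in this protocol: it steers continued enrolment (Section 5.1) and is an exploratory grading target (Sections 4.3 and 11.3). An analyst cannot drop it unannounced.

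A second reply is that *and* means both scales are required, which gives one answer. That answer is not intervenable for 50 signals without a curtain, which contradicts the count in the same sentence.

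Third, the line on core-lab grades stands under the comparison with SOC TCD, which is performed only where it is standard of care. That is so. Grading of NB-IS recordings on both scales is supported by that line together with Section 11.3, but the plan does not say outright that every subject gets both grades. Section 11.4 does not help with the choice, because it ranks core-lab over local readings and not one scale over the other.

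Finally, this is one secondary endpoint with no threshold or power attached. That is correct and limits the weight of the point.

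**Conclusion.** The concern holds. As written, the 11.2 rule is right for the SLS and wrong for the ICC, and no other section settles which governs. Recordings with more than 30 signals and no curtain are classed differently according to the reading chosen.

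The total effect is unknown because the protocol gives no distribution of counts or curtain patterns. The per-subject effect of 0.67 points (150 subjects) or 2.2 points (45 shunt-positive subjects) rests on full main-study enrolment and, for the second figure, on 30% prevalence. Agreement with TTE may move either way, and shifts may partly cancel.

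The primary endpoint, the success criteria in Section 11.5 and the sample size in Section 11.6 are unaffected. The point should be corrected before analysis but does not threaten the main result.

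**What to change.** Before analysis, reconcile Section 11.2 with Appendix 13.2. State one governing scale for this endpoint, or an explicit combination rule saying whether both or either must be met and how a curtain with 30 or fewer signals is handled. Tabulate the other scale descriptively. Say whether the unilateral doubling rule applies here. Use one label for the endpoint in the synopsis, Section 4.2 and Section 11.2.

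Because the count and the citation in the sentence match the SLS alone, removing the mention of the ICC from it is the smallest edit that makes it consistent; any other explicit rule would also cure the defect. This concerns the analysis definition only and says nothing about which shunts should be treated.

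The cost is about one sentence and one extra table from core-lab grades, provided all NB-IS recordings are graded on both scales. If a single scale is chosen, the other becomes descriptive for this endpoint.
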